If the participant consents to participate, the study staff will administer three tests to determine the participant's final eligibility for study involvement. These include: Mini Mental Status Exam,¹² the Short Physical Performance Battery (SPPB)¹³ and the 400 meter walk test.¹⁴ Those eligible will have the choice of continuing with the baseline assessment during the screening visit or returning for the baseline assessment during a subsequent visit. All baseline and one-year assessments (described below within *study procedures*) will occur at Spaulding Cambridge. Participants will undergo the initiation of the exercise/technology training with a licensed physical therapist at one of two locations: Spaulding Cambridge Outpatient Clinic (SCOC) or the Center for Neurorehabilitation at the College of Health and Rehabilitative Sciences, Sargent College, Boston University. Participants will choose their location based on geographical convenience initially until it is necessary to assign them in order to achieve equal participant numbers at each location.

V. STUDY PROCEDURES

Enrolled participants will complete in-person assessments at baseline and 12 months at SCOC. The main study outcome will be the Late Life Function and Disability Index (LLFDI).¹⁵ Additional assessments include: Hopkins Verbal Learning Test¹⁶, Trail Making (Parts A and B)¹⁷, Digit Symbol Substitution Test¹⁸, Katz Comorbidity Questionnaire¹⁹, depression (PHQ-9)²⁰, Activities Specific Balance Scale (ABC)²¹, Barriers Specific Self-Efficacy Scale²², Computer Attitude Scale,²³ McGill Pain Map,²⁴ Brief Pain Inventory²⁵, Figure 8 walk test,²⁶ Grip Strength testing with a hand-held dynamometer(Jamar),²⁷ Single leg press strength and speed testing,²⁸ ankle/knee ROM,²⁹ the Trunk extensor endurance test³⁰, 4-step stair climb and stair climb power test.³¹ All questionnaire completion will be done at a slow enough pace so as not to tire individuals. To minimize subject burden during the assessment visits, staff will provide ample time for breaks and resting between assessments. All physical performance tests will be initiated by a demonstration of technique and

REACH (Rehabilitation Enhancing Aging through Connected Health): Detailed Protocol

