an initial repetition/trial of minimal effort in order to ensure familiarity and safety with the procedures. If research staff deems a participant cannot perform a task safely, would be at risk for injury or could exacerbate an existing condition, then the participant will not perform that task. If adverse symptoms or potentially serious side effects develop during any of the testing, procedures will be terminated immediately. Participants may refuse any assessment. During the 12 month visit, assessments may be prioritized and the visit abbreviated based upon the corresponding needs and safety concerns of participants. Study participants who report being unable to do in-person office visits at 12 months may be offered the option of having a home visit conducted by the physical therapist or research assistant. Additionally, those who are unable to do a home visit may be offered the option of doing a phone interview.

At approximately 3 months, 6 months, and 9 months, study staff will contact participants over the phone to administer questions. Participants will be asked to self-report recent falls, hospitalizations, emergency room visits and prescribed physical therapy (*outside of the REACH intervention that is described in more detail below). During the 6 month phone call, study staff will also conduct the Late Life Function and Disability Index (LLFDI)¹⁵ over the phone. Since, the participants will still be participating in PT visits associated with the REACH intervention at the approximate 6 month time point the licensed physical therapist will perform the following performance based assessments during one of their clinic visits: SPPB¹³ and ankle/knee ROM²⁹. Information regarding the participant's performance will be shared with the participant for the purpose of: (1) providing feedback regarding functional performance changes, (2) enhancing participant motivation to continue to exercise and (3) promoting behavioral change for the adoption of a long term exercise habit.

REACH (Rehabilitation Enhancing Aging through Connected Health): Detailed Protocol

Table 2: REACH Data Collection Time Table (*in addition to PT intervention)

Assessment	Estimated duration of testing (minutes)	Screen	Baseline	3 Month (Phone)	6 Month (in person & phone)	9 Month (Phone)	12 Month
Informed Consent	30	X					
MMSE	5	X					X
SPPB	10	X			X		X
Long Distance Corridor Walk	15	X					X
Demographic & Health History Questionnaire	5		X				
Technology Experience Survey	2						X

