Physical Activity Item	1		X				
Katz Comorbidity	15		X				
Height/Weight & Vitals	5		X				X
Cognitive Testing Hopkins Verbal Learning Test Trail Making Digit Symbol Substitution Test	20-30		X				X
PHQ-9	5		X				X
History of Falls/Hospitalizations/ER/PT	5		X	X	X	X	X
Global measures of function & disability	2		X				X
LLFDI	30		X		X		X
Self-efficacy ABC scale Barriers Specific	15		X				X
Brief Pain Inventory	5		X				X
McGill Pain Map	5		X				X
Computer attitude scale	2		X				X
Grip Strength	5		X				X
Figure 8	5		X				X
Trunk Extensor Endurance	5		X				X
Range of Motion	10		X		X		X
Leg Strength/Power	20		X				X
Stair Climb	5		X				X
4-Step Stair Climb	5		X				X
Visit Total Time		~ 1 hr	~ 2.5- 3 hr	5 min	~ 1 hr	5 min	~ 3.5- 4 hr

REACH (Rehabilitation Enhancing Aging through Connected Health): Detailed Protocol

Upon completion of the baseline assessment, participants will be assigned to either the Boston University or Spaulding Cambridge Outpatient Clinic training site to begin the REACH model of rehabilitative care.

Participants will participate in an average of 8-10 clinic or home visits that can be increased up to 16 total visits as needed and interspersed over a 9-month period with a physical therapist licensed in MA. During the clinic/home visits, the assigned exercises are video recorded using the Wellpepper clinician version of the exercise application housed on an iPad mini. During and after the in-person visits, the PTs will remotely monitor exercise adherence, provide feedback, progress the exercise program and answer participants' questions using the chat feature of the Wellpepper application. PT support will be tapered over the course of this nine-month period as the participants become more successful at integrating exercise into their lives. Over the final three months of the study (months 10-12), subjects will continue to use the iPad and the Wellpepper application to perform their exercises independently. The PT will not initiate communication with the participants; however, PT support will be available through the chat feature if participants have questions or concerns.

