Participants are introduced to the Wellpepper iPad platform early in the intervention phase of the study to ensure they are adequately trained on proper use of the iPad and the exercise application. When the iPad is issued to the participant, their responsibilities will be reviewed again and they will be asked to sign a form indicating that they understand and agree with their responsibilities (see the submitted REACH iPad Information and Responsibility form). The participant will receive a copy of the form and the original form will be kept in a locked cabinet in the research office at the Cambridge study site. Each participant will understand that the iPad is to be returned upon treatment completion or early withdrawal. Participants will be told that there will be no financial consequences if the issued iPad is damaged, lost or stolen, but that they should handle the iPad carefully and keep it secured against theft.

[figure not shown]
Home visits are interwoven among the clinic visits to foster integration of the exercise program into daily routines with the support and guidance of a physical therapist. Optimizing exercise performance and strategizing overcoming barriers to exercising to facilitate long-term engagement in exercise will be a primary focus of the home visits. The specific number of visits and the location of the visits will be determined by the participant and the physical therapist.

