Regarding home exercise compliance, the expectation is that the participant will comply with the assigned videotaped exercises, 5 days a week for 30 minutes each session throughout the duration of the 12 months that they are active in the study. Participants may exceed the recommendation if they so choose. The physical therapist will be monitoring participant home exercise compliance through the in-person visits and the Wellpepper App. While a 5 times per week exercise schedule is the ultimate goal, we understand that this may not be feasible for all participants or it may take time to work up to this frequency. In addition, we realize that illness or other events may interfere with regular exercise performance. Therapists will be working with each participant to help them achieve the 5 times per week goal. The PT will receive an alert when a participant has not performed their assigned exercises for more than one week. The PT will communicate with the participant by phone or through the Wellpepper App chat feature to determine the reason for non-compliance. Non-compliance with the assigned exercises will not be grounds for study dismissal. We recognize that exercising once per week is better than not exercising at all. Our intent is to encourage increased exercise performance through the enhanced communication feature of the iPad and the Wellpepper app, not penalize a participant in any way for non-compliance.

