data, including Medicare claims. Brandeis has a long standing relationship with the Center for Medicaid and Medicare Services and houses a large volume of administrative claims that are used for a variety of evaluation and development activities.

We will not be recruiting a control group, but selecting a matched group of participants from the Boston RISE cohort study as controls for aim 1, which focuses on functional outcome measures. The Boston RISE cohort study is a longitudinal cohort study evaluating mobility decline among older primary care patients. Boston RISE contains all of the primary and secondary outcome measures of the study. For outcomes utilizing Medicare Claims data, data is only available for a geographic region encompassing a minimum of 250,000 individuals. Thus, for aims 2 and 3, our collaborators at Brandeis will also identify a second matched control group based upon scientifically relevant data elements, such as age, gender, race, chronic conditions, etc.

VI. BIOSTATISTICAL ANALYSIS

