This quasi-experimental study will use a difference-in-difference (D-in-D) approach to assess the impact of mHealth supported PT compared to treatment as usual. We will use a strong matching algorithm, such as exact matching on age, sex and the propensity to participate in treatment, to ensure comparability on observable characteristics between treatments and control group members. For this study the propensity score serves as a form of data reduction, taking many diagnostic flags and reducing them to a single covariate. The basic model estimates the effect of treatment on the change in outcome between baseline and follow-up: $y_{it} = \beta_0 + \beta_1 treatment_i + \beta_2 post_{it} + \beta_3 treatment_i * post_{it} + \gamma controls_{it} + \alpha_i + \varepsilon_{it}$ where y_{it} is cost, $\gamma controls_{it}$ are patient socio-demographic characteristics and $treatment_i$ is a 0/1 variable indicating treatment status. β_3 is the parameter of interest, capturing the joint effect of being in the treatment group at time 2. For the first study object, this model can be extended to include repeated measures of functional status over time. This is a proof of concept pilot study and thus we may not be powered to observe statistically significant differences among our outcomes between groups. However, the effect sizes will be utilized to inform the design of larger trials. For example, meaningful differences in the LLFDI have been published by our group and will help interpret the magnitude of treatment effects observed.

VII. RISKS AND DISCOMFORTS

Common risks and discomforts

All of the proposed measures have been validated among older adults of varying health status. The staff has extensive experience conducting these measures safely among older adults with mobility problems. Many of the assessments for this study involve minimal risk to the participants such as questionnaires, measures of leg strength and power using a double leg press machine, measurement of core muscle weakness, performance of simple balance testing, standing up from a chair, walking eight feet, and balancing with feet in a tandem position. Thus the risks are expected to be similar to those risks involved in participating in a physical therapy program, standing, stair climbing, walking, and activities of daily living. The balance and walk tests could potentially result in a fall, but the protocol includes careful personal monitoring during the

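### The protocol permits, without requiring, a participant's own treating therapist to collect the main outcome at the 12-month fallback home visit

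*Combined protocol and SAP*

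**What the plan says.** Section V (Study Procedures) names the outcome: "The main study outcome will be the Late Life Function and Disability Index (LLFDI"). Table 2 schedules it at baseline, 6 months and 12 months. For participants who cannot come to the clinic at 12 months, the same section allows "having a home visit conducted by the physical therapist or research assistant", and a phone interview if a home visit is not possible either. It does not list which measures a home visit keeps, and it does not say who assesses at the ordinary 12-month clinic visit or by phone.

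Elsewhere in Section V the unqualified term means the clinician giving that participant's care. On the intervention home visits: "The specific number of visits and the location of the visits will be determined by the participant and the physical therapist". On adherence: "The physical therapist will be monitoring participant home exercise compliance through the in-person visits and the Wellpepper App".

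The order of events and the source of controls are also in Section V: "Upon completion of the baseline assessment, participants will be assigned to either the Boston University or Spaulding Cambridge Outpatient Clinic training site" to start treatment, and "We will not be recruiting a control group", with Aim 1 controls matched from Boston RISE. Section VI (Biostatistical Analysis) makes β3 the parameter of interest, "capturing the joint effect of being in the treatment group at time 2".

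Section IX (Monitoring and Quality Assurance) requires staff and therapists to show competence, to be trained on standardized materials, and to have forms checked weekly. It does not separate those who treat from those who assess.

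**The concern.** Staff administer the LLFDI, but the participant supplies the answers. By month 12 a participant may have had 8 to 16 visits with one therapist and months of remote contact. When that therapist asks the questions, the participant may wish to report success, and the therapist may hope to hear it. The likely direction is towards better function, though the documents cannot confirm this.

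The influence would be one-sided. Baseline is collected before treatment starts, and no Aim 1 control has a REACH therapist. Neither the before-after difference nor the comparison with controls would cancel it. Section VI plans to use the effect sizes in designing larger trials, so a systematic shift could carry into that planning.

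**Working it through.** The documents give no expected number of home visits, no LLFDI standard deviation, no assessor effect and no sample-size calculation. There is no stated figure to reproduce, and the main check is textual.

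**Text.**

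1. *Can the home visit include the LLFDI?* Yes. It is due at month 12, and study staff give it by phone at 6 months, so it does not need the clinic. The 12-month visit may be shortened, so inclusion is possible rather than certain.
2. *Does the wording cover the treating therapist?* Yes, on its natural reading, given how Section V uses the term. At 6 months the licensed therapist also measures SPPB and range of motion during an intervention visit.
3. *Does it require that person?* No. The research assistant is the stated alternative. Section IV (Subject Enrollment) also lets a physical therapist take consent before a training site is assigned, so a non-treating therapist is possible.
4. *Does any other rule exclude the treating therapist?* None was found. Section IX covers competence, training and form checks. The research assistant named in Section VII (Risks and Discomforts) covers the corridor walk only.

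**Where the influence would land.** Let a share *f* of REACH participants be assessed at 12 months by their own therapist. Let *b* be the mean shift in their answers relative to what another assessor would have obtained. REACH baseline and both RISE values are untouched, so

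shift in β3 = *f* × *b*.

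**Illustration (all inputs assumed).** The unit is one SD of 12-month LLFDI change. Take *f* = 5–30% (0.05 × 76 ≈ 4 to 0.30 × 76 ≈ 23 participants) and *b* = 0.1–0.3 SD. For the standard error, assume 76 versus 76 with all assessed, equal SDs and no within-pair correlation: √(2/76) = 0.162 SD.

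| *f* | *b* (SD) | Shift in β3 (SD) | Shift ÷ 0.162 |
|---|---|---|---|
| 0.05 | 0.1 | 0.005 | 0.03 |
| 0.10 | 0.2 | 0.020 | 0.12 |
| 0.20 | 0.3 | 0.060 | 0.37 |
| 0.30 | 0.3 | 0.090 | 0.55 |

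*b* must be read as net. A research assistant also knows that every recruited participant was treated, so only the excess due to the treating relationship can be removed.

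**What an absolute bar could cost.** Suppose barring the therapist meant that *k* participants went unassessed, that their true change was 0.3 SD worse than the rest (assumed), and that all controls were kept. The REACH mean would then rise by (*k*/76) × 0.3:

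- *k* = 4: 0.016 SD
- *k* = 8: 0.032 SD
- *k* = 15: 0.059 SD

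These lie within the range of the influence itself, so the rule should not cause missed assessments.

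**Precision of a matched-pair sensitivity analysis.** Dropping *k* pairs gives a standard error of √(2/(76 − *k*)). For *k* = 4 this is √(2/72) = 0.167 SD; for *k* = 23 it is √(2/53) = 0.194 SD.

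**The case against.** The strongest case for leaving the text alone is that the exposure is slight and its size is assumed. The home visit is an optional fallback in a proof-of-concept pilot that disclaims power. The LLFDI is answered by the participant, not scored from performance. Assessors are trained and their forms checked. In months 10–12, "The PT will not initiate communication with the participants". A research assistant would be unblinded too, and an assessor restriction could lose the least mobile participants.

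Most of this stands. It limits the size, and the risk of lost assessments is why the fix keeps a last-resort exception. It does not remove the gap. Participant-reported answers can still be influenced by who asks. Training does not change the treating relationship. The limit on therapist-initiated contact concerns support, does not bar an assessment visit, and leaves chat open.

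A reader might infer more: that the protocol assigns outcome assessment to treating therapists, or that the Aim 1 result will be materially biased. The documents support neither. The wording is permissive, names an alternative assessor, and gives no frequency or effect size.

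**Conclusion.** The point holds as a cheap improvement that should be made. The protocol permits a participant's own therapist to collect the main outcome at the 12-month home visit, and it names no assessor for the clinic visit or phone interview. Any treating-therapist influence would enter β3 undiluted by the control group.

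The size cannot be derived from the documents and is probably small. The range of 0.005–0.09 SD rests wholly on the assumed share and shift, and its ratio to the standard error also assumes 1:1 matching. It shows scale and is not an estimate. The case for change is that the remedy costs little, not that a large bias is expected.

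**What to change.** In Section V, state that the 12-month LLFDI and other outcome assessments, whether in clinic, at home or by phone, are done by the research assistant already named or by other existing staff not treating that participant. Allow the treating therapist only if the assessment would otherwise be missed.

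Record assessor and mode (clinic, home, phone) at 12 months. If any treating-therapist assessments occur, show a sensitivity analysis without those participants and their matched RISE controls. It stands beside the main result and does not replace it, because the participants left out are likely to be less mobile than the rest.

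The cost is one sentence, two recorded fields and slightly less scheduling flexibility for home visits. The documents do not give research-assistant capacity, which is why other staff and the last-resort exception are included. The sensitivity analysis loses the precision shown above. The change does not blind the assessor, since every recruited participant is treated; it removes only the treating relationship.

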REACH (Rehabilitation Enhancing Aging through Connected Health): Detailed Protocol

I. BACKGROUND AND SIGNIFICANCE

a. Historical background

For older adults, a decline in mobility skills is a signal event, identifying higher risk for disability and increased healthcare utilization. Whatever the cause, the decline or loss of the ability to walk safely, climb stairs or get up from a chair (collectively termed “mobility skills”) are signal events. Without detection and intervention, deterioration of mobility skills can begin an inexorable downward spiral leading to dependency, morbidity, increased health care utilization and mortality.^{1,2} On the basis of 20 years of research in this area, we know that mobility limitations are largely preventable and there are opportunities for improving outcomes and access to quality focused care in both healthy and chronically ill older adults. It is estimated that without establishment of new care paradigms specific to treating mobility limitations that these problems alone will add an estimated \$42 billion to health care costs by 2040.² Currently there is no drug therapy for mobility limitations and the most efficacious treatment is rehabilitative care.

Health care and health care financing in this country are largely predicated on a medical model which prioritizes acute, disease-specific conditions, and on the provision of medical and surgical interventions. However, it has been demonstrated that for older adults, following disease specific guidelines is a major cause of adverse health outcomes and increased costs of care.³ In contrast, rehabilitative care treats the functional consequences of diseases and conditions, directly addressing individual needs using a comprehensive integrated approach to preserve and improve physical function. Access to high quality rehabilitation services is a major gap in our fragmented healthcare system. There are no established models that focus on treating and preventing mobility decline or that can be scaled to the varied populations of older adults residing in the US.^{1,4}

b. Previous pre-clinical or clinical studies leading up to, and supporting the proposed research

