The proposed pilot study will evaluate the benefit of this care program on physical function and health care utilization. The resulting findings have the potential to change how mobility care is provided and thus to prevent mobility decline in older adults and broadly impact national healthcare reform initiatives.

II. SPECIFIC AIMS

For older adults, a decline in mobility skills is a signal event, identifying higher risk for disability and increased healthcare utilization. Based upon the collective research and clinical experience of our multidisciplinary team, we are proposing an innovative rehabilitative care program for older primary care patients at risk for mobility decline. The program targets newly identified risk factors for mobility decline and utilizes mobile health technology to deliver patient centered care more efficiently. The program is consistent with Medicare funded services, but uses a number of innovations such as mobile health technology to demonstrate the potential for long term benefit. This proof of concept quasi-experimental trial will evaluate the benefit of this unconventional care program on physical function and health care utilization after one year of follow up.

Our project will evaluate three main objectives:

1. In comparison to matched controls derived from the Boston RISE cohort study, we will evaluate the benefit of our mobility care program on **physical function** among 76 older adults at risk for mobility decline after one year of follow up.
Hypothesis: In comparison to controls, participants in our mobility care program will have significantly greater improvements in physical function after one year of follow up.
2. In comparison to matched controls derived from Medicare claims data, we will evaluate the impact of our mobility care program on **health care utilization** after one year of follow up.
Hypothesis: In comparison to controls, participants in our mobility care program will have significantly fewer hospitalizations and ED visits after one year of follow up.
3. In comparison to matched controls derived from Medicare claims data, we will evaluate the impact of our mobility care program on **health care costs** after one year of follow up.
Hypothesis: In comparison to controls and after accounting for the estimated per patient costs of our intervention, participants in our mobility care program will have significantly lower healthcare costs after one year of follow up.

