REACH (Rehabilitation Enhancing Aging through Connected Health): Detailed Protocol

III. SUBJECT SELECTION

This proof of concept quasi-experimental pilot study will evaluate the benefit of a novel rehabilitative care program on physical function and health care utilization after one year of follow up. We will recruit 76 community dwelling older adult primary care patients.

Inclusion criteria:

1. Age \geq 65-95 years
2. Able to understand and communicate in English
3. Difficulty or task modification with walking $\frac{1}{2}$ mile (6 blocks) or climbing one flight of stairs
4. Ability to continuously walk 400 m in less than 15 minutes without stopping for more than a minute at a time, sitting, leaning, or the help of another person
5. Lives in a zip code within 10 mile radius of Spaulding Cambridge Facility
6. Baseline Short Physical Performance Battery (SPPB) scores from 3-12 with <20% of SPPB scores in the 11-12 range

Exclusion Criteria:

1. Presence of a terminal disease (e.g. receiving hospice services, metastatic cancer)
2. Major surgery or Myocardial Infarction in the last 6 months
3. Planned major surgery (e.g. joint replacement)
4. Planned move from the Boston area within 1.5 years
5. Mini-mental state exam (MMSE) score <20
6. Major medical problems interfering with safe and successful testing (examples may include: history hip replacement with recurrent dislocation, uncontrolled hypertension, use of supplemental oxygen)

Recruitment procedures will follow the same methodology utilized within the previously IRB approved Boston RISE cohort study.⁷ Prior to contacting any potential participants, [name] and his staff will convene educational sessions with clinicians from participating primary care practices at Mass General Hospital in order to familiarize their staff with the study. To facilitate continued and regular support with recruitment throughout the course of the study, [name] and his research coordinator at MGH primary care are collaborators. They will facilitate recruitment from primary care clinics within the MGH healthcare systems.

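### The Medicare claims controls for Aims 2 and 3 are not shown to represent usual care for mobility-limited, community-dwelling patients, so parallel trends in utilization and cost cannot be assumed

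*Combined protocol and SAP*

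**What the plan says.** Section II sets the population for all three aims: "we are proposing an innovative rehabilitative care program for older primary care patients at risk for mobility decline". Section III makes that concrete: "We will recruit 76 community dwelling older adult primary care patients". Entry requires "Difficulty or task modification with walking" half a mile or climbing one flight of stairs, completion of a 400 m walk, and "Baseline Short Physical Performance Battery (SPPB) scores from 3-12". An MMSE below 20, terminal disease, and major surgery or myocardial infarction in the previous 6 months all exclude. Primary care physicians also strike out patients they think unsuitable.

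The two control groups are built differently. Aim 1 controls come from Boston RISE, a mobility-decline cohort of older primary care patients. For Aims 2 and 3, section V says that the collaborators will "identify a second matched control group based upon scientifically relevant data elements, such as age, gender, race, chronic conditions, etc", using claims from a region of at least 250,000 people.

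Section VI states the contrast as the programme against treatment as usual, estimated by difference-in-difference. Its example of a matching algorithm is exact age and sex plus the propensity to participate. The score is described as "taking many diagnostic flags and reducing them to a single covariate". Model covariates are socio-demographic, with a person-level effect. The claims request described in section V covers the study year and 6 months of run-out.

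**The concern.** Matching only on the elements the plan names yields controls who resemble participants in demographics and diagnoses but were not selected for mobility limitation. The protocol gives a reason why that matters for these outcomes. Section I says that "a decline in mobility skills is a signal event, identifying higher risk for disability and increased healthcare utilization", and goes on to describe deteriorating mobility as something that can start a progression towards greater utilization. If so, untreated mobility-limited people may have a steeper one-year change in use than people matched on diagnoses alone.

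A second gap runs the other way. Participants have no terminal disease and live in the community, but no such limit is written for the controls. Any control near the end of life or in long-term institutional care whose use rises after the index date would make the programme look beneficial.

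Both errors would enter the interaction coefficient. Section VI intends to use the effect sizes to plan larger trials, and a reader could not tell from the estimate which error dominated.

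**Working it through.** The plan gives no utilization rate, control ratio or power calculation for Aims 2 and 3, so there is no stated figure to reproduce. The check compares the texts and then illustrates scale with assumed inputs.

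**1. Participant limits against control definition**

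| Section III or recruitment limit | Stated for claims controls? | Visible in claims? |
|---|---|---|
| Community-dwelling primary care patient | No | In part (facility residence, primary care visits) |
| Self-reported walking or stair difficulty | No | No; partial proxies only |
| 400 m walk, SPPB 3-12, MMSE of at least 20 | No | No |
| No terminal disease | No | Largely (hospice claims, metastatic-cancer diagnosis) |
| No major surgery or MI in 6 months | No | Yes |
| Physician judges patient suitable | No | No |

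**2. What difference-in-difference leaves.** The person effect and the group term absorb constant level gaps. With a true effect of zero, what remains is:

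bias = (expected change in untreated participants) - (expected change in controls).

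A negative value looks like benefit.

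**3. Mobility component (all inputs assumed).** Let untreated mobility-limited people rise by g1 over the year, others by g0, from the same baseline mean, and let a share q of controls be limited. Then bias = (1 - q)(g1 - g0).
- g1 = 20%, g0 = 5%: q = 0, 0.3, 0.5 gives +15%, +10.5%, +7.5% of the baseline mean.
- g1 = 10%, g0 = 5%: +5%, +3.5%, +2.5%.
- g1 = g0, or q = 1: zero.

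**4. Hospice or institutional component (all inputs assumed).** Let a share p of matched controls go from b to k times the eligible mean, with everyone else unchanged. Then bias = -p(k - b).
- b = 2, k = 4: p = 2%, 5%, 8% gives -4%, -10%, -16%.
- b = 1.5, k = 3: -3%, -7.5%, -12%.
- k = b, or p = 0: zero.

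**5. Both together, as admissions.** Let r be the baseline rate (0.2 to 0.3 per person-year), g the growth in mobility-limited people (0 to 30%, none in others), m the share of controls who are limited (0.3 to 1), and t the share of terminal controls (0 to 5%), each gaining 1 admission. Then bias = rg - [(1 - t)mrg + t].
- Most positive: r = 0.3, g = 0.3, m = 0.3, t = 0 gives 0.09 - 0.027 = +0.063, or 21% of r.
- Most negative: g = 0, t = 0.05 gives -0.05, which is 25% of 0.2 or 17% of 0.3.
- Cancellation: r = 0.2, g = 0.2, m = 0.3 gives 0.04 - 0.012 = +0.028 at t = 0. At t = 0.03 it is 0.04 - (0.97 × 0.012 + 0.03) = -0.002. At t = 0.05 it is 0.04 - (0.95 × 0.012 + 0.05) = -0.021.

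A few percentage points in one unknown share therefore reverse the sign.

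**6. Against sampling noise.** Assume Poisson counts, independent periods and unlimited controls. The standard error of the mean change in 76 participants is sqrt(2r/76): 0.073 at r = 0.2 (36% of r) and 0.089 at r = 0.3 (30%). The extremes in step 5 are about 0.7 of a standard error (0.05/0.073 and 0.063/0.089).

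**7. Baseline.** The model needs a pre-period outcome, but the claims request in section V names none. As written, the plan does not show that baseline use can be differenced, matched on or checked for prior trend.

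**The case against.** The matching list is open, and section VI offers its algorithm only as an example, so the analysts may intend restrictions and proxies they did not write down. A participation score containing cancer flags would give people with metastatic disease a propensity near zero, so few would be matched. The section I sentence about higher risk can be read as a difference in level, which difference-in-difference removes; the passage on progression gives neither a size nor a one-year timescale. Participants must complete a 400 m walk, so they are not the most impaired. The study is a proof-of-concept pilot whose main outcome is the LLFDI. It claims comparability only on observed characteristics and warns of low power. Step 6 shows that even the extreme assumed biases fall below one standard error.

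Most of this stands as a limit on how strongly the point can be put. A reader might infer that the comparator is a different population, that it contains terminal or nursing-home residents, or that the estimate is biased in a known direction. The documents support none of these: they are silent on the control restrictions rather than admitting such people.

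It does not remove the point. An open list permits a suitable comparator but does not secure one. Hospice enrolment and facility residence are not diagnoses, so diagnostic flags alone may miss them. No functional proxy is named. Low precision does not excuse bias, which would not shrink if the design were scaled up.

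**Conclusion.** The concern holds in limited form. On the elements the plan names, the Aims 2 and 3 comparator is not shown to represent usual care for community-dwelling, mobility-limited older primary care patients, and parallel trends cannot be taken for granted given the protocol's own account of mobility decline. The mobility gap is the stronger part. The hospice and institutional gap is weaker, because the propensity score may already exclude many such controls.

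The net sign and size cannot be determined from the documents. Every growth rate, share and utilization multiple above is assumed, and the illustrations include cases with no bias. They show only that plausible departures could run either way and offset each other. The change is worth making before controls are drawn, because the comparator is otherwise left open and the utilization and cost effect sizes may feed into later trials.

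**What to change.** - **Section V, control groups.** Before matching, assign each potential control an index date. Restrict the pool to beneficiaries who meet the section III limits that claims can show: no hospice claim, no metastatic-cancer diagnosis, and no major surgery or MI in the prior 6 months. Also require no long-stay nursing-facility residence and a primary care visit in the prior year. Supplemental oxygen should not become a hard exclusion, since section III gives it only as an example of a problem that may interfere with testing.
- **Section VI.** Add to the propensity score claims indicators of mobility limitation and frailty (gait or walking-difficulty diagnoses, fall injury, walking-aid or wheelchair claims, home health use, dementia diagnosis) and pre-index utilization. Report balance on each after matching.
- **Section V, claims request.** Extend it to a pre-index period for both groups, which the restrictions, the score and the difference-in-difference baseline all need.
- **Interpretation.** State that self-reported difficulty, the 400 m walk, SPPB and MMSE cannot be matched in claims, so the estimate is relative to claims-similar beneficiaries.

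The cost is revised wording, extra claims programming, a wider data request and a somewhat smaller control pool. No new participants or visits are needed. The proxies capture mobility limitation only in part, so some residual difference will remain.
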